6.6.1 Adverse events

Missing or incomplete AE dates are imputed according to BI standards ([2](#)).

Proprietary confidential information © 2017 Boehringer Ingelheim International GmbH or one or more of its affiliated companies

6.6.2 Laboratory values at baseline

For missing laboratory data at Cycle 1 Visit 1 (before the very first administration of study medication) data from preceding visits will be used.

6.7 BASELINE, TIME WINDOWS, AND CALCULATED VISITS

6.7.1 Baseline

The last measurement observed prior to start of trial medication will be assigned to baseline. Note that for some trial procedures (for example body weight, vital signs, laboratory tests) this may be the value measured on the same day trial medication was started. In these cases it will be assumed that the measurements were taken prior to the intake of any study medication. For tumour assessment, baseline evaluations must be based on Magnetic Resonance Imaging (MRI) or Computed Tomography scans performed no more than 30 days prior to start of trial medication.

Study days and visits will be labelled according to the flow chart of the CTP.

Unless otherwise specified, baseline is defined as the latest time-point before the very first administration of any study medication. If this criterion is not fulfilled then no baseline will be derived.

Laboratory values:

Baseline is defined as the latest time-point before the very first administration of any study medication.

If any of these times are missing and the date of laboratory value is equal to the date of first study drug administration, then the laboratory assessment will be considered as according to protocol, i.e. as prior to first study medication.

6.7.2 Time windows for every RECIST assessment

In order to identify whether consecutive imaging time-points are missing for a given patient, a nominal time point [4, 8, 16, 24, 32, 40, 48, 56, 68 weeks and every 12 weeks thereafter] will be assigned to each and every image. This is achieved by creating windows for every RECIST assessment. The windows are defined in Table 6.7.2: 1 below. Day 1 corresponds to the date of first drug intake of xentuzumab or afatinib.

Table 6.7.2:1 Nominal time-points and windows for imaging

Nominal time-point [weeks from start of therapy]	Due date of scans [days]	Window [days]
4	29	1 to =< 43

Proprietary confidential information © 2017 Boehringer Ingelheim International GmbH or one or more of its affiliated companies

8	57	44 to =< 85
16	113	86 to =< 141
24	169	142 to =< 197
32	225	198 to =< 253
40	281	254 to =< 309
48	337	310 to =< 365
56	393	366 to =< 435
68	477	436 to =< 519
every 12 week interval	etc (1)	etc (1)

(1) Due date of imaging = (nominal time point * 7) + 1. To calculate the lower bound of the window, use the middle point between the due date of the previous time point and the current due date + 1. To calculate the upper bound of the window, use the middle point between the due date of the next time point and the current due date.

If a patient does not have an image in one of the windows described above, he/she will be said to have 'missed an assessment' for that time-point. In case a patient has more than one assessment in one window, the assessment with the latest outcome will be used for the analysis unless a PD has been recorded earlier then PD will be used.

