During Follow-up, concomitant therapy only needs to be recorded if indicated for the treatment of an AE.

Tumour assessment will be performed every 4 weeks after start of treatment with Xentuzumab (BI 836845) and afatinib for first 8 weeks (prior to courses 2 and 3 ), in 8-week intervals thereafter (e.g. prior to courses 5, 7, 9, etc.) and in 12-week interval after course 16 until PD or start of further anti-cancer treatment. It should include CT scans or MRI. CT images not older than 30 days at start of treatment will suffice as screening images and don't have to be repeated. The EOT tumour assessment is optional if performed in the previous 4 weeks. Imaging may be performed within 7 days of scheduled time point. Additional imaging follow up will be required for patients who discontinued not due to progressive disease at 8-week intervals until progression, lost to follow-up or initiation of other anti-cancer treatment.

Tissue biopsies to determine EGFR mutations and other relevant pathways at study entry and following progression may be obtained after obtaining informed consent. (Optional at the time of progression) In case there is a documented result of EGFR mutations available before study entry for Part A, local result is acceptable. For Part B, tumour sample provision to central laboratory is mandatory for confirmation of the result. Prior to any biopsy, patients must have controlled hematology parameters (INR and PTT within normal range) and platelet count ( $\geq 100,000 / \mu\text{L}$ ). See [Section 4.2.2](#) for restriction of

Proprietary confidential information.

© 2016 Boehringer Ingelheim International GmbH or one or more of its affiliated companies. All rights reserved.

This document may not - in full or in part - be passed on, reproduced, published or otherwise used without prior written permission.

antiplatelet and anticoagulant medications. For tissue biopsy at the time of progression after study treatments, separate informed consent must be obtained.

Part A: afatinib intake starting from Course 1 Day 8 up to Course 2 Day 1 and Course 3 Day 1 must be recorded in the patient diary and it should be dispensed to the patient on Day 1, 8, 15 and 22 of Course 1 and Day 22 of Course 2.  
Part B: afatinib intake from Course 2 Day 1 and Course 3 Day 1 must be recorded in the patient diary and the diary card should be dispensed to patient on Day 22 of Course 1 and Day 22 of Course 2.  

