#### 5.1.2 Assessment of efficacy

The assessment by the investigator and the local radiologist will be the basis for continuation or discontinuation of the trial in an individual patient (in addition to safety).

Tumour assessment will be performed every 4 weeks after start of treatment with Xentuzumab (BI 836845) and afatinib for first 8 weeks (prior to courses 2 and 3), in 8-week intervals thereafter (e.g. prior to courses 5, 7, 9, etc.) and in 12-week interval after course 16

Proprietary confidential information.

© 2016 Boehringer Ingelheim International GmbH or one or more of its affiliated companies. All rights reserved.

This document may not - in full or in part - be passed on, reproduced, published or otherwise used without prior written permission.

until PD or start of further anti-cancer treatment. Imaging may be performed within 7 days of scheduled time point. In case of tumour response (CR or PR), confirmation will be performed with a repeat assessment no less than 4 weeks after the RECIST criteria for response have been met. In the case of SD, measurement must have met the SD criteria at least once after study entry at an interval of not less than 6 weeks.

CT/MRI images not older than 30 days at start of treatment will suffice as screening images and don't have to be repeated. The EOT tumour assessment is optional if performed within the previous 4 weeks. At baseline, the investigator along with the radiologist will record the target (five target lesions maximum and maximum two per organ) and non-target lesions at baseline in the eCRF before the start of treatment. The same method of assessment and the same technique should be used to characterise each reported lesion at baseline and during follow up. Measurable lesion should be available after tumour biopsy. Lesions in previously irradiated areas may not be considered measurable at baseline unless the lesions occurred after irradiation. Response will be evaluated according to the response evaluation criteria in solid tumours (RECIST version 1.1, [R09-0262 – Appendix 10.5](#)). In the event of a delay, interruption or discontinuation of treatment, tumour assessment should continue to follow the original schedule. The schedule should be followed until progression is observed or until the patient commences further treatment for disease, whichever occurs first.

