## 7.6 DETERMINATION OF SAMPLE SIZE

Part A follows a 3+3 design with escalating/de-escalating steps ([R07-0220](#)) for the determination of the MTD of Xentuzumab (BI 836845) in combination with afatinib. According to this design as described in [Section 4.1.3](#), up to 18 evaluable patients may be needed to identify the MTD. Six additional patients will be treated at the RP2D level before commencing Part B.

The patients in Part B will be treated at the RP2D. In the expansion cohort, 18 additional patients will be treated. Assuming a true response rate of 20% a sample size of 18 patients leads to a probability of 73% of observing at least 3 objective responses (CR or PR). If the true response rate is higher i.e. 25%, then the probability to observe at least 3 objective responses is 86%. The probability of a false positive signal is <0.1%.

True Response Rate	# Patients per cohort	Probability to observe at least				
		1 event	2 events	3 events	4 events	5 events
0.15	16	0.92575	0.71610	0.43862	0.21011	0.07905
0.15	18	0.94635	0.77595	0.52034	0.27976	0.12056
0.15	20	0.96124	0.82444	0.59510	0.35227	0.17015
0.20	16	0.97185	0.85926	0.64816	0.40187	0.20175
0.20	18	0.98199	0.90092	0.72866	0.49897	0.28365
0.20	20	0.98847	0.93082	0.79392	0.58855	0.37035
0.25	16	0.98998	0.93652	0.80289	0.59501	0.36981
0.25	18	0.99436	0.96054	0.86470	0.69431	0.48133
0.25	20	0.99683	0.97569	0.90874	0.77484	0.58516
0.01	16	0.14854	0.01093	0.00051	0.00002	0.00000
0.01	18	0.16549	0.01376	0.00073	0.00003	0.00000
0.01	20	0.18209	0.01686	0.00100	0.00004	0.00000

Altogether the total sample size is anticipated to be approximately 42 entered patients. Naturally this represents only a rough estimation since the number of patients needed is induced by the “3+3” design and is subject to different influencing factors. Assuming a 60% of screen fail rate, 105 patients are anticipated to be enrolled in the trial.

Proprietary confidential information.

© 2016 Boehringer Ingelheim International GmbH or one or more of its affiliated companies. All rights reserved.

This document may not - in full or in part - be passed on, reproduced, published or otherwise used without prior written permission.

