## Evaluation of best response to study treatment

The best response to study treatment ([Table 10.5: 3](#)) is the best response recorded from the start of treatment until disease progression or start of further anti-cancer treatment (taking as reference for progressive disease the smallest measurements recorded since the treatment started). In general, the patient's best response assignment will depend on the achievement of both measurements and confirmation criteria ([Table 10.5: 3](#)).

Patients with a global deterioration of health status requiring discontinuation of treatment without objective evidence of disease progression at that time should be reported as “symptomatic deterioration”. Every effort should be made to document the objective progression even after discontinuation of treatment.

Table 10.5: 3 Algorithm for evaluation of overall response\*

Target lesions	Non-target lesions	New lesions	Overall response
CR	CR	No	CR
CR	Non-CR/ Non-PD	No	PR
CR	Not evaluated	No	PR
PR	Non-PD or not evaluated	No	PR
SD	Non-PD or not evaluated	No	SD
Not evaluated	Non-PD	No	NE
PD	Any	Yes or No	PD
Any	PD	Yes or No	PD
Any	Any	Yes	PD

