5.2.2.2 Second part

Time to OR

Time to objective response is defined as the time from first treatment administration until first documented CR or PR.

Time to objective response will only be calculated for patients with an objective response:

- Time to OR [days] = date of first documented CR or PR - date of first treatment administration + 1.

Duration of OR

Duration of objective response is defined as the time from first documented CR or PR until the earliest of disease progression or death among patients with objective response.

Duration of objective response will only be calculated for patients with an objective response. For patients with disease progression or death:

- Duration of objective response [days] = date of outcome – date of first assessment indicating OR + 1.

For patients without disease progression or death:

- Duration of objective response (censored) [days] = date of outcome – date of first assessment indicating objective response + 1

The censoring rules for duration of OR are given in Table 5.2.2.2: 1.

Table 5.2.2.2: 1 Derivation rules for Duration of Objective Response

Situation	Outcome (event or censored)	Date of outcome
No other anti-cancer therapy		
Alive and not progressed, no more than one consecutively missed radiological assessments	Censored	Date of last radiological assessment
Alive and not progressed, two or more consecutively missed radiological assessments	Censored	Date of last radiological assessment prior to missed radiological assessments
Progressed, zero or one missed radiological assessment prior to progression	Event	Date of radiological assessment of progression
Progressed, but two or more consecutively missed radiological assessments prior to progression	Censored	Date of last radiological assessment prior to missed assessments

Proprietary confidential information © 2017 Boehringer Ingelheim International GmbH or one or more of its affiliated companies

Table 5.2.2.2: 1 Derivation rules for Duration of Objective Response (cont.)

Situation	Outcome (event or censored)	Date of outcome
Death but no progression, zero or one missed radiological assessment prior to death	Event	Date of death
Death without progression, but two or more consecutively missed radiological assessments prior to death	Censored	Date of last radiological assessment prior to missed assessments
Initiation of subsequent anti-cancer therapy		

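### The one-assessment-per-window rule in SAP 6.7.2, read literally, can undo or re-date a confirmed response on the Part B primary endpoint

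*SAP*

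**What the plan says.** SAP 6.7.2 gives the imaging windows a limited purpose: "In order to identify whether consecutive imaging time-points are missing for a given patient". Table 6.7.2:1 sets the windows; week 8 (due day 57) covers days 44–85 and week 16 (due day 113) covers days 86–141. The section then ends with a rule on outcomes: "In case a patient has more than one assessment in one window, the assessment with the latest outcome will be used for the analysis". The only exception is for progression, where an earlier PD in the window takes precedence. There is no corresponding exception for an earlier CR or PR, or for a confirmatory scan.

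Other text bears on the same data:

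- Protocol 5.1.2, for CR or PR: "confirmation will be performed with a repeat assessment no less than 4 weeks after the RECIST criteria for response have been met".
- Protocol Appendix 10.5: "the patient's best response assignment will depend on the achievement of both measurements and confirmation criteria". SAP 5.1.2 defines objective response, the Part B primary endpoint, by reference to this appendix.
- SAP 5.2.2.2: "Time to objective response is defined as the time from first treatment administration until first documented CR or PR". Duration of response starts at the same point.
- Protocol Flow Chart footnote 11 and Protocol 5.1.2: scans at weeks 4 and 8, then every 8 weeks, then every 12 weeks after course 16, each within 7 days of its due date. Footnote 11 lists no separate confirmatory scan.

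**The concern.** To count missed scans one needs to know only whether a window contains an image. Choosing which outcome to use, with a priority for PD, is not needed for that, and the analysis to which the choice applies is not restricted to censoring. A programmer could reasonably reduce the data to one assessment per window before deriving best overall response.

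That reduction conflicts with the confirmation requirement. From week 8 onwards, a site that confirms a response at about 4 weeks must add a scan. The added scan falls in the window of the first response scan, which is then dropped, or in the window of the next scheduled scan, which replaces it if done. In either case one of the two scans that establish confirmation can disappear, and the patient can become a non-responder on the primary endpoint. In milder cases only the response date moves, which lengthens time to response and shortens its duration.

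**Working it through.** **1. Windows.** Footnote (1) of Table 6.7.2:1 gives due day = 7 × week + 1, upper bound = midpoint to the next due day, and lower bound = midpoint from the previous due day, plus 1. For week 8, the due day is 57, the upper bound (57 + 113)/2 = 85 and the lower bound (29 + 57)/2 + 1 = 44. All printed bounds reproduce. For weeks 8–48 the window closes exactly 28 days after the due day, which is the minimum confirmation interval. For weeks 56 and 68 it closes 42 days after.

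**2. Worked cases.** Keep the latest scan in each window, with an earlier PD taking precedence; then require a second retained PR at least 28 days after the first.

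| Scans (day) | All scans | Kept by the rule | Result |
|---|---|---|---|
| PR 57, PR 85, PD 113 | Confirmed, day 57 | PR 85, PD 113 | Confirmation lost |
| PR 60, PR 88, PD 113 | Confirmed, day 60 | PR 60, PD 113 | Confirmation lost |
| PR 57, PR 85, PR 113 | Confirmed, day 57 | PR 85, PR 113 | Confirmed, dated day 85 |
| PR 57, PR 86, PR 113 | Confirmed, day 57 | PR 57, PR 113 | No change |
| PR 57, PR 113, PD 169 | Confirmed, day 57 | All three | No change |
| PR 29, PR 57, PD 113 | Confirmed, day 29 | All three | No change |

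In the third row, time to response is 85 − 57 = 28 days longer (28 × 12/365.25 = 0.92 months) and duration 28 days shorter.

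**3. All day combinations.** Let the first PR fall on the due day −7 to +7 (15 values) and the extra PR 28 to 35 days later (8 values), giving 15 × 8 = 120 pairs per time-point. The 7-day tolerance is the protocol's. The 35-day upper limit is an assumption, because the protocol gives only a minimum.

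- *Week 4:* 0 of 120 pairs share a window.
- *Weeks 8–48:* a first scan k days early (k = 0 to 7) shares a window with repeats at 28 to 28 + k days, which is k + 1 values. The sum is 1 + 2 + … + 8 = 36. A first scan even one day late never shares. So 36 of 120 pairs share a window and 84 do not.
- *Weeks 56 and 68:* all 120 pairs share a window.

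Now add the next scheduled scan for weeks 8–48, 56 days after the due day ±7 (15 values), giving 120 × 15 = 1,800 combinations:

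| Next scheduled scan | Effect of the literal rule |
|---|---|
| PD | Confirmation lost in 1,800 of 1,800 |
| SD | Not confirmed on the retained scans in 1,800 of 1,800 |
| PR | Unchanged in 84 × 15 = 1,260; first PR dropped in 36 × 15 = 540, of which the date moves in 372 and confirmation waits for a further scan in 168 (next scan under 28 days after the retained PR) |
| None done | Lost in 36 of 120 pairs, unchanged in 84 of 120 |

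**4. Scale in Part B.** One responder is 1/18 = 5.6 percentage points; for example, 3/18 = 16.7% becomes 2/18 = 11.1%. Protocol 7.6 describes the sample size by the chance of at least 3 responses. At a true rate of 20% this is 1 − 0.8^18 − 18(0.2)(0.8^17) − 153(0.04)(0.8^16) = 0.72866, matching the stated 73%.

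**The case against.** The strongest answer is that the literal reading is not the intended one. Section 6.7.2 opens with its own purpose, which serves the missed-assessment rows of the duration-of-response censoring table. SAP 5.1.2 takes best response over the whole period from first administration, and SAP 5.2.2.2 dates response from its first documentation; neither refers to the windows. On that reading nothing is lost, and dating a response at day 85 when PR was documented on day 57 would contradict 5.2.2.2. The public SAP also has sections removed and refers to a technical TSAP and table shells that are not available, so a governing rule may exist there.

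Further, losing a responder needs several things together: the rule applied to best response, a first response at week 8 or later, an extra scan that the Flow Chart does not list, and then either no response at the next scheduled scan or no later scan with both PRs in one window. A site may instead confirm at the next scheduled scan, in which case nothing changes. The trial is descriptive, and no decision rule is attached to the count of 3.

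These points stand as limits on likelihood and severity. They do not remove the problem: the closing sentence selects outcomes for an unrestricted analysis, protects an earlier PD but not an earlier response, and nothing in the available text says that the endpoint definitions prevail over it.

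**Conclusion.** The concern holds as an ambiguity with a real consequence; it does not show how the sponsor will program the endpoint. Read literally, the rule can turn a confirmed response into a non-response, or move its date by 28 to 35 days, when a response first seen at week 8 or later is confirmed by an extra scan about 4 weeks on. Two competent programmers could obtain different response rates from the same scans, and each patient reclassified moves the Part B rate by 5.6 points.

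The conclusion assumes that the latest outcome means the assessment latest in time, that confirmation is judged on the windowed data, and that repeats occur 28 to 35 days after the first response. The counts are of day combinations, not patient probabilities. Week-4 responses confirmed at week 8 are unaffected, and a durable response usually remains confirmed. The point should be settled before the analysis, but it does not call the design into question.

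**What to change.** Add to SAP 6.7.2 that the windows and the one-assessment-per-window rule serve only to identify missed assessments for censoring. State also that best overall response, confirmation, disease control, time to objective response and duration of objective response use every adequate tumour assessment, including confirmatory and unscheduled scans, at its actual date.

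The cost is one or two sentences and agreement with the programming specification. No new data are needed, and the sample size and its stated probabilities do not change.

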7 PLANNED ANALYSES

The labelling and display format of statistical parameters will follow BI standards (7).

Unless otherwise specified, outputs will be displayed separately for each part of the trial.

With protocol amendment 4, starting doses of xentuzamab 1000mg + afatinib 30mg and xentuzamab 1000mg + afatinib 20mg are also allowed in part B. For part B, sections for trial subjects and safety analyses will be displayed by starting dose and total. Efficacy analyses will be done for part B patients, and RP2D patients (defined as pooled patients of all the patients in part B and the patients starting with xentuzumab 1000mg + afatinib 40mg in part A excluding squamous carcinoma patients).

Descriptive statistics for continuous variables will generally contain N (number of patients in that patient set with non-missing values), Mean, Standard Deviation, Minimum (Min), Q1 (25th percentile), Median, Q3 (75th percentile), Maximum (Max). In general, means, standard deviations, medians, Q1 and Q3 will be presented to one more decimal place than the raw data. Minima and maxima will be presented to the same number of decimal places as the raw data.

For time-to-event analysis tables, the set of statistics is: number of patients [N (%)], Number of patients with event [N (%)], Number of patients censored [N (%)], <Time to event> [months] followed by P25 (25th percentile), Median, P75 (75th percentile). If not specified otherwise, the duration as well as time to event will be displayed in months.

Tabulations of frequencies for categorical data will include all possible categories and will display the number of observations in a category as well as the percentage (%) relative to the respective treatment group total. Percentages will be rounded to one decimal place.

In general a category “missing” will be displayed, if there are missing data for the corresponding variable. Percentages will also generally be based on all patients in the respective patient set whether they have non-missing values or not.

Sort order for general categorical variables: If categories correspond to the collected categories on the eCRF and the table shells do not explicitly specify the ordering, the “default ordering” defined by the eCRF is to be used in such cases. If categories are derived the ordering as specified in the table shell document should be used; in general ordinal data (e.g. categorised continuous data) are to be displayed in ascending order.

The denominator of the main categories is defined by the number of patients in the used patient set. The main categories define the denominators of the subcategories. Subcategories should be indented and “[N (%)]” to be displayed only for the main category.

If a table includes only categorical data, “[N (%)]” is to be displayed in the column header.

In general, a “Total” column will not be displayed for post-baseline displays. Tables that display the status of patients for a primary or secondary endpoint with number of events and number censored will contain a total column.

Proprietary confidential information © 2017 Boehringer Ingelheim International GmbH or one or more of its affiliated companies

Abbreviations (e.g., Wors.) or acronyms (e.g., PD) should not be displayed in tables and patients data listings without any explanation. They will be either spelled out in the table or explained in footnotes (whatever is more reasonable from the programming point of view).

If applicable, conversion from days to weeks, months and years will be as follows:

- Weeks = days \div 7
- Months = days \times 12 \div 365.25
- Years = days \div 365.25

